11.3. Subject Information

For all subjects, demographic characteristics (eg, age, height, weight, body mass index, race, and sex) and screening/baseline characteristics (eg, physical examination, medical history) will be tabulated and summarized with descriptive statistics.

11.4. Safety Analyses

No formal statistical testing of safety data is planned. Safety data will be analyzed descriptively (including 95% confidence intervals, if applicable), by cohort and overall.

Baseline for all safety parameters will be defined as the last value before the prime vaccination.

Adverse Events (Including Reactogenicity)

The verbatim terms used in the CRF by investigators to report adverse events will be coded using the Medical Dictionary for Regulatory Activities (MedDRA). All reported adverse events (solicited local, solicited systemic, and unsolicited) will be included in the analysis. For each

adverse event, the number and percentage of subjects who experience at least 1 occurrence of the given event will be summarized by group. Summaries, listings, datasets, or subject narratives may be provided, as appropriate, for those subjects who die, who discontinue study vaccine due to an adverse event, or who experience a severe or a serious adverse event.

The analysis for solicited adverse events will be done on those subjects in the Full Analysis set for whom reactogenicity assessments are available in the database. The analysis of unsolicited adverse events will be done on the Full Analysis set.

Clinical Laboratory Tests

Laboratory abnormalities will be determined according to the toxicity grading tables, and in accordance with the normal ranges of the clinical laboratory. The most severe laboratory abnormalities following vaccination will be tabulated per regimen.

Vital Signs and Electrocardiogram

Vital signs and ECG abnormalities following vaccination will be tabulated by most severe abnormality grade.

Physical Examination

Physical examination abnormalities following vaccination will be tabulated by most severe abnormality grade.

11.5. Immunogenicity Analyses

Descriptive statistics (actual values and changes from baseline, including 95% confidence intervals, if applicable) will be calculated for continuous immunologic parameters at each time point. Graphical representations of changes in immunologic parameters will be prepared, as applicable. Frequency tabulations will be calculated for discrete (qualitative) immunologic parameters at each time point. In addition, differences between the vaccination schedules will be evaluated at the 21-day post-boost, 6-month post-boost and Day 365 visits.

Integrative statistical analysis of the gene expression and functional assays and modeling analyses of data obtained in Cohort II will be detailed and reported separately from this study.

The SAP will provide details on how the samples from the subjects whose boost is out of window due to the pause are to be handled in the statistical analyses.

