2.2. Hypothesis

As this study is designed to provide descriptive information regarding safety and immunogenicity without formal treatment comparisons, no formal statistical hypothesis testing is planned.

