### 1.3. Statistical Hypotheses for Trial Objectives

As this study is designed to provide descriptive information regarding safety and immunogenicity without formal vaccination schedule comparisons, no formal statistical hypothesis testing will be performed.

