## 1.5. Randomization and Blinding

Randomization was used to minimize bias in the assignment of subjects to vaccination schedules (groups), to increase the likelihood that known and unknown subject attributes (eg, demographic and baseline characteristics) are evenly balanced across groups, and to enhance the validity of possible statistical comparisons across groups. In addition, randomization was used to minimize bias in the assignment of subjects to study vaccine (active vaccine versus placebo).

Central randomization was implemented in this study. At baseline, subjects were randomly assigned to 1 of 3 groups in a 1:1:1 ratio in Cohorts I, II, and III. Blinding procedure were not applied to Cohort I (as all subjects received Ad26.ZEBOV and MVA-BN-Filo in an open-label fashion). Cohorts II and III were blinded. Within group, subjects were randomly assigned to Ad26.ZEBOV and MVA-BN-Filo, or placebo in a 14:1 and 10:3 ratio in Cohorts II and III, respectively, based on a computer-generated randomization schedule prepared before the start of the study under the supervision of the sponsor. Subjects in Group 4 were randomly assigned (in a blinded fashion) to Ad26.ZEBOV or placebo in a 5:1 ratio. The randomization within each group was balanced by using randomly permuted blocks and was stratified by country in Cohorts II and III. Randomization in each group (for Cohorts II and III) was further stratified by age at randomization ( $\leq 50$  years,  $> 50$  years).

In Cohorts II and III, subjects and study-site personnel were blinded to the study vaccine allocation within groups until the last subject of the study completed the 6-month post-boost visit or discontinued earlier and the clinical database was locked, except for unblinded qualified study-site personnel with primary responsibility for study vaccine preparation and dispensing, and not involved in any other study-related procedure. The study vaccines were administered by a study vaccine administrator (ie, a trained study nurse, medical doctor, or otherwise qualified health care provider who had no other study function).

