## 2. GENERAL ANALYSIS DEFINITIONS

The type I error rate ( $\alpha$ ) is set to 0.05 and corresponding 2-sided 95% confidence intervals (CIs) will be calculated wherever applicable. Adjustment of the  $\alpha$  (type I error) level due to

multiplicity is not applicable for this study as no planned formal statistical hypothesis testing will be performed.

Analysis and evaluation are defined separately for each parameter later in this document together with the description of rules for handling missing or incomplete data. The analyses will include vaccinated subjects with respect to the actual vaccine administered. The subjects who were vaccinated according to MVA-BN-Filo prime/Ad26.ZEBOV boost or a homologous (ie, Ad26.ZEBOV prime/ Ad26.ZEBOV boost or MVA-BN-Filo prime/MVA-BN-Filo boost) schedule will be excluded from summary analyses (ie, tables and graphs) and listed separately.

In general, the study data will be analyzed as follows:

- Categorical variables will be summarized with a frequency table presenting counts and percentages.
- Continuous variables will be summarized using the following statistics, as appropriate: number of observations, arithmetic mean, geometric mean, corresponding 95% confidence interval (CI), standard deviation, standard error, median, quartiles (Q1 and Q3), minimum and maximum.

*Baseline value* will be defined as the value of the last available assessment performed prior to the prime vaccination, unless specified otherwise.

For safety assessments, the *baseline value* will be an assessment performed prior or on the date (if only time of assessment is missing) of the prime vaccination. The baseline value for immunogenicity assessments will be an assessment performed before or on the date of the prime vaccination. In case of multiple values, the value closest to the vaccination will be used as the baseline.

*Reference value* (only for immunogenicity) will be defined as the assessment performed on the date of the boost vaccination. In case of multiple values (on the same day of vaccination), the value closest to the vaccination will be used as the reference value.

*Visit day* will be determined relative to the actual day of vaccination (date of prime vaccination or date of boost vaccination).

Repeated assessments of immunogenicity and safety will be allocated to analysis windows and periods based on [Table 1](#) and [Table 2](#).

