#### 6.2.1.3. Analysis Methods

- The available humoral immune responses (immunogenicity against EBOV GP) will be evaluated for cohorts II and III. The pooled cohorts II and III data (ie, ELISA) will also be presented by age group. The Group 4 data will be presented separately. See

[Table 4](#) for more details.

Summary statistics (ie, geometric mean and corresponding 95% CIs) will be calculated and presented for ELISA binding antibody responses (ELISA units/mL) and VNA ( $\text{IC}_{50}$  titer) at each time point.

Regimen profiles of the geometric mean concentrations with 95% CIs will also be presented. In addition, graphs of the reverse cumulative distributions (ie, percentage of subjects versus the magnitude of the antibody response levels) will be provided for the following time points, if available:

- Baseline and pre-boost
- Baseline and 21 days post boost
- Baseline and 180 days post boost
- Baseline and Day 365 post prime

For both ELISA (ELISA units/mL) and VNA ( $IC_{50}$  titer), additional graphical representations (on a  $\log_{10}$ -scale) will be provided using dot plots (with distinction between positive and negative sample interpretations), by vaccination schedule.

Responder rates and positive sample interpretation will be summarized (ie, showing number, percentage and the exact 95% Clopper-Pearson CI) for ELISA (ELISA units/mL) antibody responses and VNA ( $IC_{50}$  titers) per time point.

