### 6.2.2.3. Analysis Methods

The cellular immune responses will be evaluated based on the Cohort II data (see [Table 4](#)).

Summary statistics (ie, median, quartiles [Q1, Q3]) will be presented for all the continuous cellular immunogenicity outcomes at each time point. Also, the median fold increases (from Pre-dose 1 and Pre-dose 2) with the corresponding quartiles (Q1 and Q3) will be presented.

Graphical representations (on a  $\log_{10}$ -scale) will be provided using dot plots (with distinction between responders and non-responders), by vaccination schedule. Also, regimen profiles of the vaccinations schedules showing the median and the quartiles (Q1 and Q3) will be presented. Responder and positive sample interpretation rates will be summarized (ie, showing number, percentage and the corresponding exact 95% Clopper-Pearson CIs) per timepoint.

The proportions of EBOV GP-specific CD4+ and CD8+ T cells (ie, cells producing at least 1 of the 3 investigated cytokines) will also be tabulated per timepoint and shown in a pie chart. The magnitude of each cytokine subset will be shown in a bar chart. Both pie chart and bar chart will be restricted to responders.

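### Protocol 11.5 promises an evaluation of differences between schedules at three visits, but the SAP defines no between-schedule estimate and does not declare the omission

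*Protocol*

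**What the plan says.** **Protocol.** Section 11.5 lists descriptive statistics, graphs and frequency tables for the immunologic parameters. As a further item it states that "differences between the vaccination schedules will be evaluated at the 21-day post-boost, 6-month post-boost and Day 365 visits". The synopsis says the same. Neither place names a parameter or an effect measure, and section 11 leaves details to the SAP. Section 11.2 sizes pairwise ELISA differences: Table 8 gives detectable log10 differences at 164 subjects per group with 90% power and a two-sided 5% level that allows for multiple testing. Section 2.2 describes the study as one "without formal treatment comparisons, no formal statistical hypothesis testing is planned".

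**SAP.** Section 1.3 describes a study "without formal vaccination schedule comparisons, no formal statistical hypothesis testing will be performed", and section 2 says of alpha adjustment that "multiplicity is not applicable for this study as no planned formal statistical hypothesis testing will be performed". For humoral outcomes, section 6.2.1.3 says: "Summary statistics (ie, geometric mean and corresponding 95% CIs) will be calculated and presented for ELISA binding antibody responses", and the same holds for VNA. It adds: "Regimen profiles of the geometric mean concentrations with 95% CIs will also be presented". Reverse cumulative curves, dot plots, and responder and positivity rates with Clopper-Pearson intervals follow. ELISA is also shown by age group (Table 4). For cellular outcomes, section 6.2.2.3 says: "Summary statistics (ie, median, quartiles [Q1, Q3]) will be presented for all the continuous cellular immunogenicity outcomes at each time point". Section 1.5 says that randomisation within each group was "balanced by using randomly permuted blocks and was stratified by country in Cohorts II and III", and further by age at 50 years. Section 3 (changes to the planned analysis) lists only the redefinition of the immunogenicity and per protocol sets.

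**The concern.** The protocol makes the evaluation of differences an item separate from the per-schedule summaries, and its sizing rests on pairwise contrasts. The SAP, which was to supply the details, contains no ratio, difference, model or contrast between schedules for any immunogenicity outcome, and does not say that this evaluation was dropped.

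The three regimens differ only in boost timing, so how the schedules compare is a natural use of the immunogenicity data. Under the SAP as written, a reader has two or three separate geometric means, each with its own interval, and no stated estimate of how far apart the schedules are or how precisely that is known. Comparing separate intervals by eye is conservative against a direct interval and gives no effect size.

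**Working it through.** **1. What the sizing assumed.** Inputs from Protocol 11.2: n = 164 per group, SD 0.5 to 1.2 log10, 90% power, two-sided 5% with a multiplicity allowance whose method is not given. Formula: difference = SD × (z for alpha + z for power) × √(2/n).

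- Unadjusted alpha 0.05: 0.179 at SD 0.5 rising to 0.430 at SD 1.2. This does not match Table 8.
- Bonferroni over three pairs (0.05/3): SD × (2.394 + 1.282) × √(2/164) = 0.406 × SD, giving 0.203, 0.244, 0.284, 0.325, 0.365, 0.406, 0.447 and 0.487. Rounded from unrounded values, all eight rows match (0.20, 0.24, 0.28, 0.32, 0.37, 0.41, 0.45, 0.49).
- Tukey gives 0.361 at SD 0.9 and 0.401 at SD 1.0, against 0.37 and 0.41 in the table.

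Table 8 is therefore consistent with three explicit pairwise contrasts. The protocol's statement of at least 80% power after the cut in Group 3 also reproduces: 82.7 to 85.0% with 121 in Group 3, and 80.5 to 82.9% with 111.

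**2. Separate intervals against a direct interval.** For two independent schedules with equal n and SD:

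- half-width of the 95% CI for the difference = 1.960 × SD × √(2/n);
- gap at which two separate 95% CIs stop overlapping = 2 × 1.960 × SD/√n;
- ratio = 2/√2 = 1.41, whatever n and SD.

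In standard errors of the difference, non-overlap needs 1.960 × √2 = 2.77. Against the Bonferroni-over-three critical value of 2.394 the ratio is 2.77/2.394 = 1.16. As a two-sided level, 2.77 corresponds to 0.0056.

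**3. Absolute widths (illustrative).** SAP 1.4 gives only a total of about 423; evaluable numbers per schedule are not stated. The range shown is an assumption: 164 is the planned number in Cohorts II and III; 111 is Group 3's 121 less 10 from Cohort I (assuming the 121 includes Cohort I, as 174 = 10 + 84 + 80 does); 50 stands for heavy loss to late or missed boosts. The same n is taken in both groups, and SD is 0.5 log10, the lowest in Table 8.

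| n per schedule | Half-width for difference, log10 (fold) | Gap for non-overlap, log10 (fold) | Chance of seeing a true 0.20 log10 difference: direct 95% CI excludes zero / separate CIs do not overlap |
|---|---|---|---|
| 164 | 0.108 (1.28) | 0.153 (1.42) | 95% / 80% |
| 111 | 0.132 (1.35) | 0.186 (1.53) | 85% / 58% |
| 50 | 0.196 (1.57) | 0.277 (1.89) | 52% / 22% |

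At SD 1.2 the half-widths are 0.260, 0.316 and 0.470 log10.

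**4. Time since boost at Day 365.** This visit is counted from the prime dose. On schedule, the boost was 365 − 29 = 336, 365 − 57 = 308 and 365 − 85 = 280 days earlier in Groups 1, 2 and 3.

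**The case against.** The best defence is that both documents call the study descriptive and disclaim formal comparisons, and that Protocol 11.5 names no measure, so evaluation could mean side-by-side display. SAP 1.4 adds that the halt makes the planned regimens hard to evaluate, and Protocol 3.2 looks to other studies for more data on them. This explains having no test. It does not explain having no estimate: a ratio with a 95% CI is descriptive, and SAP section 2 already plans 95% CIs without testing. Amendment 5, which stopped enrolment because of the delays, left the sentence in 11.5.

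Several stronger readings are tempting and are not supported:

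- **That the secondary objective goes unanswered.** That objective is to assess the ELISA response to each schedule at 21 days post boost, and per-schedule means with CIs address it. ELISA at the other two visits is exploratory. The gap is against 11.5.
- **That the randomisation strata are ignored.** ELISA is presented by the age stratum. Country is pooled (SAP 2.2), and no between-schedule estimate adjusts for either factor.
- **That the SAP tells readers to judge by overlap.** It sets no such rule. The factor of 1.4 describes a likely reading habit. Its benchmark is also debatable: against nine contrasts (three pairs at three visits), 0.05/9 = 0.0056 is the same level as non-overlap.
- **That a ratio would be a clean randomised contrast.** The per protocol set drops boosts outside the window, and Group 3 randomisation stopped at Amendment 4 while UK screening restarted for Groups 1 and 2.

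It also stands that a reader given n, means and CIs could work out an unadjusted ratio by hand. That is not a specified analysis, and it cannot recover an adjusted one.

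**Conclusion.** The point holds as an undeclared mismatch between protocol and SAP: the evaluation of differences promised in 11.5 has no estimate to deliver it. It should be corrected, but it does not undermine the per-schedule results or the primary safety analysis.

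The firm part of the size is relative: 1.4 times the unadjusted interval, or 1.16 times the Bonferroni-over-three interval, for equal n and SD. The absolute widths depend on an evaluable n that the documents do not give and on Table 8's SD range, and intervals after exclusions may well be wider than Table 8 suggests. Attributing Table 8 to Bonferroni over three is an inference from the match in all rows, not something that the protocol states.

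**What to change.** Add to SAP 6.2.1.3, for active recipients in Cohorts II and III: the three pairwise ELISA geometric mean ratios between schedules, with 95% CIs, at 21 days post-boost, 6 months post-boost and Day 365, labelled descriptive and unadjusted for multiplicity. A linear model on log10 ELISA with schedule, country, age stratum and cohort is preferable, as these are the factors within which subjects were randomised; the protocol does not prescribe a model, so this is one reasonable choice. Report on the per protocol set and repeat on the immunogenicity set, stating whether schedule means the randomised group or the actual-interval group of SAP Table 3.

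Add notes to the table:

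- only the 21-day ELISA is a secondary endpoint;
- time since boost differs by schedule at Day 365;
- late or missed boosts and the early stop of Group 3 limit a randomised interpretation. The immunogenicity set brings back late boosts, but SAP 2.3 keeps measurements after a planned boost that was not given out of the tables.

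If the sponsor prefers not to add the ratios, SAP section 3 should state that the evaluation was dropped and why.

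Cost: SAP wording and one table, with no new data and no hypothesis test. The downside is nine unadjusted intervals per analysis set (three pairs × three visits), which the label must make plain.

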11.6. Interim Analyses

Interim analyses may be performed during the study for regulatory purposes or for the purpose of informing future vaccine-related decisions in a timely manner. The results will not influence the conduct of the study in terms of early termination or later safety or immunogenicity endpoint assessments.

A separate SAP will be prepared before the conduct of an interim analysis.

11.7. Independent Data Monitoring Committee

An IDMC will be established to monitor safety data on an ongoing basis to ensure the continuing safety of the subjects enrolled in this study. The committee will meet periodically to review interim data. Ad hoc IDMC meetings may be requested via the sponsor for any single event or combination of multiple events which are considered to jeopardize the safety of the subjects. After the review, the IDMC will make recommendations regarding the continuation of the study. The details will be provided in a separate IDMC charter.

The IDMC will be appointed by the sponsor with recommendations from the Clinical Steering Committee (see Section 11.8) before the start of the study. The IDMC will consist of at least one medical expert in the relevant therapeutic area and at least one statistician. The IDMC responsibilities, authorities, and procedures will be documented in its charter.

11.8. Trial Management Team and Clinical Steering Committee

Oversight of the study will be conducted by the Trial Management Team which will consist of members from the sponsor as well as key collaborators from participating countries. This Trial Management Team will be responsible for protocol development and ensuring proper study execution.

As part of the consortium agreement between the sponsor, INSERM and the London School of Hygiene and Tropical Medicine, a Clinical Steering Committee with representatives from each consortium partner has been established to guide the overall clinical development plan, including this study. The Clinical Steering Committee is responsible for overseeing the EBOVAC2 collaboration activities and for making decisions on specific issues.

12. ADVERSE EVENT REPORTING

Timely, accurate, and complete reporting and analysis of safety information from clinical studies are crucial for the protection of subjects, investigators, and the sponsor, and are mandated by regulatory agencies worldwide. The sponsor has established Standard Operating Procedures in conformity with regulatory requirements worldwide to ensure appropriate reporting of safety information; all clinical studies conducted by the sponsor or its affiliates will be conducted in accordance with those procedures.

12.1. Definitions

12.1.1. Adverse Event Definitions and Classifications

Adverse Event

An adverse event is any untoward medical occurrence in a clinical study subject administered a medicinal (investigational or non-investigational) product. An adverse event does not necessarily have a causal relationship with the treatment. An adverse event can therefore be any unfavorable and unintended sign (including an abnormal finding), symptom, or disease temporally associated with the use of a medicinal (investigational or non-investigational) product, whether or not

related to that medicinal (investigational or non-investigational) product. (Definition per International Council for Harmonisation [ICH])

This includes any occurrence that is new in onset or aggravated in severity or frequency from the baseline condition, or abnormal results of diagnostic procedures, including laboratory test abnormalities.

Note: The sponsor collects adverse events starting with the signing of the ICF (refer to Section 12.3.1, for time of last adverse event recording).

Serious Adverse Event

A serious adverse event based on ICH and EU Guidelines on Pharmacovigilance for Medicinal Products for Human Use is any untoward medical occurrence that at any dose:

- Results in death
- Is life-threatening
(The subject was at risk of death at the time of the event. It does not refer to an event that hypothetically might have caused death if it were more severe.)
- Requires inpatient hospitalization or prolongation of existing hospitalization
- Results in persistent or significant disability/incapacity
- Is a congenital anomaly/birth defect
- Is a suspected transmission of any infectious agent via a medicinal product
- Is Medically Important*

*Medical and scientific judgment should be exercised in deciding whether expedited reporting is also appropriate in other situations, such as important medical events that may not be immediately life threatening or result in death or hospitalization but may jeopardize the subject or may require intervention to prevent one of the other outcomes listed in the definition above. These should usually be considered serious.

If a serious and unexpected adverse event occurs for which there is evidence suggesting a causal relationship between the study vaccine and the event (eg, death from anaphylaxis), the event must be reported as suspected unexpected serious adverse reaction (SUSAR) (even after the study is over, if the sponsor, IDMC or investigator becomes aware of them) by the sponsor to the Health Authorities and by the investigator to the IEC/IRB according to regulatory and local requirements.

Unlisted (Unexpected) Adverse Event/Reference Safety Information

An adverse event is considered unlisted if the nature or severity is not consistent with the applicable product reference safety information. For Ad26.ZEBOV and for MVA-BN-Filo, the expectedness of an adverse event will be determined by whether or not it is listed in the Investigator's Brochures and Addenda, if applicable.

Adverse Event Associated With the Use of the Study Vaccine

An adverse event is considered associated with the use of the study vaccine if the attribution is **possibly**, **probably**, or **very likely** by the definitions listed in Section 12.1.2, Attribution Definitions.

Immediate Reportable Events

The following list of neuroinflammatory disorders are categorized as IREs, and should be reported to the sponsor within 24 hours of becoming aware of the event using the IRE Form. Relevant data from the IRE Form will be captured in the clinical database.

- Cranial nerve disorders, including paralyses/paresis (eg, Bell's palsy)
- Optic neuritis
- Multiple sclerosis
- Transverse myelitis
- Guillain-Barré syndrome, including Miller Fisher syndrome, Bickerstaff's encephalitis and other variants
- Acute disseminated encephalomyelitis, including site specific variants: eg, non-infectious encephalitis, encephalomyelitis, myelitis, myeloradiculomyelitis
- Myasthenia gravis and Lambert-Eaton myasthenic syndrome
- Immune-mediated peripheral neuropathies and plexopathies (including chronic inflammatory demyelinating polyneuropathy, multifocal motor neuropathy and polyneuropathies associated with monoclonal gammopathy).
- Narcolepsy
- Isolated paresthesia of >7 days duration

Symptoms, signs or conditions which might (or might not) represent the above diagnoses, should be recorded and reported as IREs even if the final or definitive diagnosis has not yet been determined, and alternative diagnoses have not yet been eliminated or shown to be less likely. Follow-up information and final diagnoses, if applicable, should be submitted as soon as they become available.

If the IRE is also serious (serious adverse event), it will also be reported using the same process as for other serious adverse events.

